3.3.1 Experimental Design

Patients with 6-month post-treatment daytime sleepiness, snoring, and sleep-related quality of life measurements will be counted for statistical analyses as non-responders under the following circumstances:

- a. Death (any cause) between treatment and the 6-month follow-up
- b. Unsuccessful radiofrequency treatment attempt
- c. Need for an alternative OSA treatment before the 6-month follow-up
- d. Subjects who abandon RAMOSA study
- e. Subjects who exit the study after the last treatment, but before the 6-month follow-up

A specific description of analyses of the above secondary endpoints is given below.

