3 HYPOTHESES AND DATA ANALYSIS

3.1 Primary Efficacy Endpoints

The primary effectiveness of the study is to demonstrate a clinically significant reduction of OSAS from Baseline PSG sleep study to the 6-month follow-up PSG in adults (≥ 22 years) with obstructive sleep apnea (AHI 10-30) and BMI ≤ 32 .

Effectiveness of the CelonProSleep *plus* will be assessed by demonstrating adequate reduction in AHI and ODI as defined below:

A responder to the CelonProSleep *plus* RFA treatment is defined as a patient with an AHI reduction $\geq 50\%$ **and** a reduction of their ODI $\geq 25\%$ at the 6-month follow-up PSG, and their AHI at the 6-month follow-up is < 20 .

The aim of the study is to show that at least 50% of participants met the primary endpoint above. This will be tested with one sided 97.5% confidence interval with $\pm 20\%$ margin of error^{73, 74}.

In order to record and analyze data for determining the primary endpoints, patients will undergo a PSG sleep study to establish a mean baseline AHI and ODI. Patients will then be treated with a series of three treatments of upper airway radiofrequency ablation with the bipolar electrosurgical electrode CelonProSleep *plus* (Olympus Winter & Ibe, Germany) over 18 weeks. The patient will undergo a second PSG sleep study at the final follow-up examination 6-months later. Mean changes in AHI will be compared for each individual and among all patients. Surgical success is defined if at least 50% of participants experience at least 50% reduction in AHI and 25% reduction in ODI (Performance Goal, PG=50%).

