3.4 Secondary Endpoints

Secondary endpoints will be examined to provide additional support and details of the primary endpoint findings concerning the RFA treatment. The secondary endpoints assess important patient-based clinical outcomes to compliment the biophysiological primary outcomes. It will be evaluated using mean change at 6-months follow-up from baseline. As supporting evidence, this will be tested with one-sided confidence interval with no corrections for multiple testing.

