3.4.1.2 Objective and Hypotheses

The FOSQ secondary endpoint in this study will be determined by the FOSQ score at the 6-month follow-up compared with the pre-treatment Baseline. The objective is to demonstrate an improvement of daytime sleepiness measured by the FOSQ.

$$H_0: \mu_{FOSQ} \leq 0$$

$$H_A: \mu_{FOSQ} > 0,$$

where μ_{FOSQ} is the mean change of FOSQ from pre-treatment baseline to the 6-month post-treatment follow-up. This hypothesis will be tested using one-sided 95% confidence interval around the mean FOSQ.

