3.4.2.2 Objective and Hypotheses

The ESS secondary endpoint in this study will be determined by the ESS score at the 6-month follow-up compared with the pre-treatment Baseline. The objective is to demonstrate an improvement of daytime sleepiness measured by the ESS.

$$H_0: \mu_{ESS} \leq 0$$

$$H_A: \mu_{ESS} > 0,$$

where μ_{ESS} is the mean change of ESS from pre-treatment Baseline to the 6-month post-treatment follow-up. This hypothesis will be tested using one-sided 95% confidence interval around the mean ESS.

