3.4.3.2 Objective and Hypotheses

Seite 23 von 54

Protocol 990211 RAMOSA

RFA for multi-level OSA

Protocol version 6.0 from 26th September 2014

The VAS_{snoring} secondary endpoint in this study will be determined by the VAS score at the 6-month follow-up compared with the pre-treatment Baseline. The objective is to demonstrate a reduction in snoring.

$$H_0: \mu_{VAS} \geq 0$$

$$H_A: \mu_{VAS} < 0,$$

where μ_{VAS} is the mean change of VAS from pre-treatment Baseline to the 6-month post-treatment follow-up. This hypothesis will be tested using one-sided 95% confidence interval around the mean VAS_{snoring}.

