8.2 Additional Analysis

Demographic, medical history and operative characteristics will be summarized for the study cohort, by clinical site, and by groupings of all sites. At a minimum, this will include age, gender, race, weight, and BMI.

Supporting analyses will be conducted to provide additional information on the safety and efficacy of multi-level radiofrequency treatment. Descriptive statistics will be utilized to summarize all adverse events. Regression models evaluating the change of continuous outcomes of AHI and ODI as well as logistic regression for the categorical outcome of response to treatment as defined in the primary objective will be used. A description of the relationship between BMI change and effectiveness outcomes will be performed by a cross-tabulation of BMI change versus responder and non-responder groups.

Data collected on all enrolled study subjects will be analyzed on an intend-to-treat and as-treated basis. Disease information and demographic variables, such as age, ethnic group, and sex, will be summarized by means of summary statistics. A normality distribution test (Kolmogorov-Smirnov) will be performed for all variables. Simple descriptive statistics such as frequency, mean, standard deviation, minimum, and maximum will be calculated for all outcome variables. If these variables are not normally distributed, other descriptive measurements such as median and the interquartile range will be calculated. For comparison between pre- and post-treatment variables, McNemar's-will be used with categorical variables. For continuous variables, a paired t-Test (normal distribution) or a Wilcoxon signed rank Test (not normal distribution) will be used to compare data at visit 2 (Baseline) and at visit 6 (six weeks after final RFA treatment). In addition, for long longitudinal analysis a One-Way ANOVA with Repeated Measures (or mixed models) will be used to model the outcome and cofactors over the multiple time-points. Significant interactions will be followed up using post-hoc analysis with Holms' adjusted P-values.

Site homogeneity will be evaluating by testing the interaction term in the analysis of covariance (ANCOVA) at a significance level of 0.15.

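### Section 3.3.1 labels failures as non-responders on secondary endpoints that are analysed only as mean changes, so the rule assigns no value and cannot be run as written

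*Combined protocol and SAP*

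**What the plan says.** Section 3.3.1 opens with patients who have six-month measurements of sleepiness, snoring and sleep-related quality of life. It says that they "will be counted for statistical analyses as non-responders under the following circumstances". Five circumstances, a to e, follow: death, an unsuccessful radiofrequency attempt, need for another OSA treatment, abandoning the study, and "Subjects who exit the study after the last treatment, but before the 6-month follow-up". The section then says that the specific analyses come next.

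Those analyses are all of means. Section 3.4 says of the secondary endpoints: "It will be evaluated using mean change at 6-months follow-up from baseline". For FOSQ (3.4.1.2): "This hypothesis will be tested using one-sided 95% confidence interval around the mean FOSQ". For ESS (3.4.2.2): "This hypothesis will be tested using one-sided 95% confidence interval around the mean ESS". For snoring (3.4.3.2) the parameter "is the mean change of VAS from pre-treatment Baseline to the 6-month post-treatment follow-up", again with a one-sided 95% interval.

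The only responder definition is the primary composite in section 3.1, where a responder to "RFA treatment is defined as a patient with an AHI reduction" of at least 50%, together with an ODI reduction of at least 25% and a six-month AHI below 20.

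Three other sections bear on the point:
- **8.4** restricts the Full Analysis Set to treated subjects who completed all eight visits.
- **8.5** classes subjects lost to follow-up as treatment failures and makes their exclusion a sensitivity analysis.
- **8.2** calls for both intention-to-treat and as-treated analysis, and adds that a "One-Way ANOVA with Repeated Measures (or mixed models) will be used to model the outcome" over the several time points.

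**The concern.** A mean change needs a number for each patient. Non-responder is a category, and the plan attaches no score to it on the ESS, FOSQ or snoring scale. The rule's starting population also contradicts its list, because patients who died or left before six months have no six-month measurement.

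The rule evidently intends failures to count against the treatment. If it cannot be executed, whoever runs the analysis must decide, possibly with the data in hand, whether these patients are omitted, imputed or entered as observed. Section 3.4 presents these endpoints as support for the primary finding in an open-label, single-arm study. The size of the mean improvement should therefore not depend on an unstated choice.

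**Working it through.** **1. Can the rule be executed?** Each provision that might supply a value was checked.

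| Place | What it offers | Value on ESS, FOSQ or snoring VAS? |
|---|---|---|
| 3.1, 8.1 | Responder on AHI and ODI | No |
| 3.3 | Percentages among the descriptive statistics | No cut-off given |
| 8.2 | McNemar's test for categorical variables | No categorical secondary outcome defined |
| 8.2 | Intention-to-treat analysis | No imputation method |
| 8.2 | Paired test | Compares Visit 2 with Visit 6 (six weeks), not six months |
| 8.2 | Repeated-measures ANOVA or mixed model | Not tied to the six-month hypotheses |
| 8.5 | Losses are treatment failures | Category only |
| 13.4 | Withdrawals for therapy failure are included in analysis | No score |

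None fills the gap.

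**2. Who is affected, and how?** Deaths and exits (a, e), and usually those who abandon the study (d), have no six-month score. Under the set in 8.4 they leave the mean. Patients under b and c may stay and supply six-month scores. Those scores would enter as observed, and for c they may reflect the other therapy.

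**3. Size.** The plan states no figure for these endpoints. Its enrolment figure reproduces: 43/(1 − 0.10) = 47.8, rounded up to 48 (section 3.2).

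Assume that all 48 are treated, that a fraction d has no six-month score, and that their true mean change is zero. Then all-treated mean = (1 − d) × completer mean, and the ratio of completer to all-treated mean is 1/(1 − d).

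- d = 0.10 (section 3.2): 1/0.90 = 1.11. In whole patients, 48/43 = 1.12.
- d = 0.247 (section 2.5, studies with follow-up to 12 months): 1/0.753 = 1.33. In whole patients, 48/36 = 1.33.

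**4. Effect on the test.** The documents give no SD for these scales, so a standardised completer change e of 0.3 to 0.8 (SD 1) is assumed. With c completers and m = 48 − c patients set to zero:
- completer t = e√c
- all-treated mean μ = e·c/48
- sum of squares = (c − 1) + c(e − μ)² + mμ²
- t = μ / √(sum of squares / (47 × 48))

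For e = 0.5 and c = 43: μ = 0.448; sum of squares = 42 + 0.117 + 1.003 = 43.12; t = 3.24, against 0.5√43 = 3.28 for completers.

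| c | e | Completer t | Zero-change t | Lower 95% bound, completer | Lower 95% bound, zero-change |
|---|---|---|---|---|---|
| 43 | 0.3 | 1.97 | 1.96 | 0.044 | 0.039 |
| 43 | 0.5 | 3.28 | 3.24 | 0.244 | 0.216 |
| 43 | 0.8 | 5.25 | 5.08 | 0.544 | 0.480 |
| 36 | 0.3 | 1.80 | 1.79 | 0.018 | 0.014 |
| 36 | 0.5 | 3.00 | 2.92 | 0.218 | 0.159 |
| 36 | 0.8 | 4.80 | 4.46 | 0.518 | 0.374 |

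The estimate and its bound shrink, but the t statistic hardly moves, because the added zeros also reduce the SD. This arithmetic covers only patients without a six-month score. The documents give no expected number under b and c who would have one.

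**The case against.** The strongest reply is that this is a wording gap in supportive endpoints, and that its consequences are easy to overstate. Much of that stands.

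- **A reader might infer that the plan prescribes completer means.** It does not say so. Section 8.4 points that way, but the intention-to-treat wording in 8.2 and the exclusion sensitivity analysis in 8.5 point towards keeping losses in. Completer means are one possible default among conflicting provisions.
- **A reader might infer that every failure disappears from the mean.** Circumstances b and c do not imply missing data. Section 13.7 allows withdrawal only at the patient's request, so such patients may complete the study. The opening words of 3.3.1 make sense for them.
- **A reader might infer that improvement is necessarily overstated.** Section 2.5 reports a prior study whose authors thought that symptom-free patients were the least likely to return. That would push a completer mean the other way.
- **A reader might place percentage sleep time with SaO2 below 90% under the rule.** Section 3.3.1 does not name it.
- **The 11% and 33% follow from the zero-change assumption.** The larger figure uses dropout from studies with follow-up to 12 months, whereas this trial follows for six months and plans for 10%.

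A mixed model alone would not answer the concern. Under missing-at-random it projects patients who leave along the course of those who stay, and it uses scores recorded after another therapy. It does not count failures as failures.

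None of this supplies the missing value. The rule still cannot be run.

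**Conclusion.** The point holds for ESS, FOSQ and snoring VAS. Section 3.3.1 applies a binary label to endpoints analysed only as means, with no threshold and no assigned score, and its starting population excludes some of the patients it lists. Under the Full Analysis Set of 8.4 the intended penalty is lost for patients without six-month data, and 8.5 conflicts with that outcome. For patients under c who stay, the plan does not say whether scores affected by another therapy count.

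The bias is upward if the patients lost are failures, and uncertain for ordinary dropout. Assuming zero change in those omitted, the overstatement is about 11% at the planned dropout and about 33% as an upper illustration. The size of effect and its confidence bound are affected more than significance. Scores worse than baseline in those omitted would widen the difference. The documents do not support extending the point to the primary responder test, which does not depend on this rule. This should be corrected, but it does not threaten the trial's main conclusion.

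**What to change.** 1. In section 3.3.1, replace the non-responder label for ESS, FOSQ and snoring VAS with a value: change from baseline is set to zero for any patient meeting circumstances a to e, whether or not a later score exists. Remove the restriction to patients with six-month measurements.
2. State that this analysis includes all treated patients, and reconcile it with the Full Analysis Set in 8.4.
3. Report two supporting analyses: the observed-case mean, which is the exclusion analysis already in 8.5, and the mixed model already named in 8.2, using all collected visits.
4. For percentage sleep time with SaO2 below 90%, which 3.3.1 does not cover and which rests on two sleep studies, report the observed change and the same zero-change analysis beside it.

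The cost is revised wording and a short additional analysis. No new data are needed, because ESS, FOSQ and snoring VAS are already collected at baseline and repeatedly through Visit 7 (Appendix I). The estimated mean improvement may be somewhat smaller.

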3.4 Secondary Endpoints

Secondary endpoints will be examined to provide additional support and details of the primary endpoint findings concerning the RFA treatment. The secondary endpoints assess important patient-based clinical outcomes to compliment the biophysiological primary outcomes. It will be evaluated using mean change at 6-months follow-up from baseline. As supporting evidence, this will be tested with one-sided confidence interval with no corrections for multiple testing.

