3.3 Secondary Efficacy Endpoints

To determine whether multi-level radiofrequency ablation of the upper airway in adults with OSAS with the CelonProSleep *plus* bipolar electrode improves daytime sleepiness, snoring, percentage sleep

time at $\text{SaO}_2 < 90\%$, and sleep-related quality of life without a significant increase in pain, speech or swallowing dysfunction.

The following tools will be applied in order to determine the secondary aims: (1) Epworth Sleepiness Scale (ESS); (2) Functional Outcomes of Sleep Questionnaire (FOSQ), (3) SaO_2 , and (4) 100 mm VAS scale concerning snoring. ESS, FOSQ, and $\text{VAS}_{\text{snoring}}$ will be assessed at Baseline, 6 weeks after completion of each upper airway RF ablation treatments, and 6 months post-treatment. The percentage sleep time with $\text{SaO}_2 < 90\%$ will be determined at the final 6-month PSG.

Secondary endpoint statistical analysis includes descriptive statistics of percentages, Means and SD; In cases in which inference will be added to the value, it will be then corrected with Holm's adjustment for testing multiplicity.

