3.4.4.2 Objective and Hypotheses

The SaO₂ secondary endpoint in this study will be determined by the SaO₂ percentage time below 90% during the 6-month PSG sleep study compared with the PSG sleep study at Baseline. The objective is to demonstrate a decrease in SaO₂ percentage time at 6-months.

$$H_0: \mu_{SaO_2\%time} \leq 0$$

$$H_A: \mu_{SaO_2\%time} > 0,$$

where $\mu_{SaO_2\%time}$ is the mean change in Percentage time with SaO₂ below 90% from Baseline to the 6-month follow-up. This hypothesis will be tested using one-sided 95% confidence interval around the mean SaO₂.

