3.5 Safety and tolerability of RFA Treatment

Safety of radiofrequency treatment will be assessed via the description of all reported adverse events. Adverse events will be summarized by seriousness, severity, relatedness to the procedure and temporal relationship to the procedure. Acute adverse events are those within 14 days of each radiofrequency treatment, long-term adverse events are those events occurring from two weeks following the final treatment until the final 6-month follow-up. No formal statistical hypotheses will be tested.

RFA specific adverse events and complications will be defined as follows (modified after Kezirian et al., 2005)⁴⁵:

- Minor: mucosal ulceration, mucosal crusting, or uvular sloughing,

- Moderate: hemorrhage that is controllable at the office, nerve paresis, or dysphagia to solid food,
- Severe: palatal fistula, hemorrhage requiring hospitalization, nerve paralysis, dysphasia requiring tube feeding, and serious infection or airway compromise requiring hospitalization or surgical intervention.

Tolerability of RFA treatment will be determined with various 100 mm VAS scales concerning pain, speech, and swallowing in order to capture patients' perceived pain, and level of speech and swallowing functions after each RFA treatment. The VAS scales will be scored by the patient immediately following each RFA procedure and 1, 3 and 7 days post-procedure. The use and amount of narcotic pain medication (hydrocodone-acetaminophen 5mg/325mg; Maximum 2 tablets every 6 hours, or 8 tablets per day; Narco®) by pill count will be recorded after each treatment. Mean score and the 95% confidence interval for the tolerability VAS scales at each RFA visit will be calculated to capture tolerability profile.

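### Sections 3.3 and 3.4 give opposite multiplicity rules for the same four secondary endpoints, and the hypothesis for sleep time below 90% saturation points away from its own objective

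*Combined protocol and SAP*

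**What the plan says.** **Two rules for one set of endpoints.** Section 3.3 lists ESS, FOSQ, oxygen saturation and the bed partner's snoring VAS as the secondary measures. It plans descriptive statistics and adds: "In cases in which inference will be added to the value, it will be then corrected with Holm's adjustment for testing multiplicity". It gives no level, sidedness or family. Section 3.3.1 closes with "A specific description of analyses of the above secondary endpoints is given below". Section 3.4 then plans mean change at 6 months and says: "As supporting evidence, this will be tested with one-sided confidence interval with no corrections for multiple testing".

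**The tests.** Each endpoint has a null, an alternative and a decision rule:
- FOSQ (3.4.1.2), alternative: mean change above 0. "This hypothesis will be tested using one-sided 95% confidence interval around the mean FOSQ"
- ESS (3.4.2.2), alternative: mean change above 0. "This hypothesis will be tested using one-sided 95% confidence interval around the mean ESS"
- Snoring VAS (3.4.3.2), alternative: mean change below 0. "This hypothesis will be tested using one-sided 95% confidence interval around the mean VAS"
- Percentage of sleep time below 90% saturation (3.4.4.2), alternative: mean change above 0, again with a one-sided 95% interval. The aim begins "The objective is to demonstrate a decrease in" that percentage.

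**Nearby text.** Section 3.5 treats the pain, speech and swallowing scales descriptively: "Mean score and the 95% confidence interval for the tolerability VAS scales at each RFA visit will be calculated to capture tolerability profile". Section 8.2 plans tests of visit 2 against visit 6, and mentions Holm only for post-hoc work after significant interactions.

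**The concern.** Section 3.3 makes Holm conditional on inference being done. The four hypotheses in section 3.4 are inference, so the condition is met, and an analyst cannot follow both sections. An endpoint with a one-sided p-value between 0.0125 and 0.05 is positive under 3.4, but may fail under Holm at one-sided 5%, depending on the other three p-values. A plan that supports both outcomes leaves the choice open until the results are known.

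The direction problem is separate. Sections 3.4.3.2 and 3.4.4.2 both define change from baseline to 6 months and both aim for a reduction, yet their alternatives have opposite signs. Tested as printed, an improvement in desaturation time cannot support its own alternative. No multiplicity rule repairs a test that points the wrong way.

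**Working it through.** **Inputs from the documents.** Four endpoints (3.3); one-sided 5% each (3.4.1.2 to 3.4.4.2); 43 evaluable patients (3.2). The plan states no family-wise error for the secondary endpoints, so there is no figure of that kind to reproduce. The 43 does reproduce: the z-test of 50% first reaches 1.96 at 28 responders of 43, with exact alpha 0.0330 and power 0.8081 at 70%, as printed in 3.2.

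**Assumptions.** Common correlation ρ from 0 to 0.9; Holm at family-wise one-sided 5%; paired t with 43 complete pairs; a higher FOSQ score is better, as its alternative implies. The documents give none of these for the secondary endpoints.

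**1. Chance of at least one false claim, k tests, all nulls true.**

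1 − ∫ φ(u) Φ((c − √ρ·u)/√(1−ρ))^k du, with c = 1.645 uncorrected. At ρ = 0 this is 1 − 0.95^k.

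| Case | ρ = 0 | 0.5 | 0.9 |
|---|---|---|---|
| Four tests, all directed at improvement, uncorrected | 18.5% | 14.4% | 8.8% |
| Same, Holm (first step 0.05/4 = 0.0125) | 4.9% | 4.1% | 2.5% |
| FOSQ and VAS only, uncorrected | 9.8% | 8.8% | 6.8% |

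The third row is the false-benefit risk with directions as printed, if both ESS and desaturation time are reversed: rejecting either of those would claim worsening. If only desaturation time is reversed, three tests can yield a false benefit claim: 1 − 0.95³ = 14.3% at ρ = 0, and 8.0% at ρ = 0.9.

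**2. Where the two rules disagree.** With 42 degrees of freedom, the critical t is 1.682 at 0.05 and 2.325 at 0.0125. Dividing by √43 = 6.557 gives 0.26 SD and 0.35 SD. An observed mean improvement between these passes under 3.4 but not at Holm's strictest step.

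**3. Power per endpoint** (noncentral t, noncentrality d·√43):

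| True improvement | Uncorrected 0.05 | Holm's strictest step 0.0125 |
|---|---|---|
| 0.3 SD | 61% | 37% |
| 0.5 SD | 94% | 83% |

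**4. Desaturation time as printed.** A true 0.3 SD reduction has noncentrality −0.3 × 6.557 = −1.97. The probability that t exceeds +1.682 is 0.00017, about 0.02%.

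**The case against.** The best defence is that the two sections differ in scope. Section 3.3.1 points forward to the specific description, and 3.4 then gives a reason for not correcting: the endpoints are supportive. On that reading Holm covers inference elsewhere. This is a sensible intention, and uncorrected supportive endpoints are acceptable when a plan says so once. But no section states that precedence, and 3.3 names the same four endpoints. Section 8.2 does not settle it, since it attaches Holm only to post-hoc tests after interactions. What stands is that one sentence limiting the scope of Holm would be enough.

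Three stronger readings are tempting and are not supported:
- A reader might infer that the plan as printed carries a 13.6% to 18.5% risk of a false benefit claim. Those are the chances of any false rejection with ESS and desaturation time both reversed (ρ = 0.9 and 0). At ρ = 0.9, 6.8% + 6.8% = 13.6%, so half of it is false claims of worsening. The figure also needs the ESS to be reversed.
- A reader might take the ESS reversal as proven. Section 7 describes the ESS as rating the tendency to fall asleep, which suggests that higher is worse, but the scoring direction is not stated. Only the desaturation hypothesis contradicts its own text.
- A reader might add the visit 6 tests to form a larger Holm family. Section 8.2 refers to continuous variables in general, so the documents define no such family.

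**Conclusion.** The conflict is real and should be resolved before analysis. Uncorrected testing of the four endpoints, all directed at improvement, carries an 18.5% to 8.8% chance of at least one false benefit claim (correlation 0 to 0.9, all nulls true), against at most 5% under Holm. With directions as printed, and the ESS taken as reversed, the false-benefit risk comes from FOSQ and snoring VAS alone and is 9.8% to 6.8%. The reversed hypothesis for time below 90% saturation is an error in its own right, whichever multiplicity rule is kept.

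The rates are worst cases over the nulls and depend on the assumed correlation. The power figures depend on 43 complete pairs and a paired t; section 8.2 allows a Wilcoxon test for non-normal data, and section 3.3.1 counts dropouts as non-responders without saying how that enters a mean change. The conflict and the reversed sign depend on none of this. Section 3.4 presents the endpoints as supportive, and neither the primary analysis nor the sample size is touched.

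**What to change.** 1. **Directions.** In 3.4.4.2, reverse the null and alternative to match the stated decrease. Confirm the ESS scoring direction; if higher means sleepier, reverse 3.4.2.2 as well.
2. **One multiplicity rule.** Choose one option:
   - **A.** In 3.4, replace the statement of no correction by Holm over the four 6-month tests at a stated family-wise level, for example one-sided 5%. Make the adjusted p-values decisive in 3.4.1.2 to 3.4.4.2, and name that family and level in 3.3.
   - **B.** Keep the uncorrected one-sided intervals as supportive only. State that section 3.4 yields no confirmatory significance claim, and limit the Holm sentence in 3.3 to inference outside 3.4.
3. **Visit 6.** State in 8.2 that the visit 2 versus visit 6 comparisons are exploratory.

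**Cost.** Text edits only, with no new data. Under A, power per endpoint at Holm's strictest step falls from 94% to 83% at 0.5 SD and from 61% to 37% at 0.3 SD, under the assumptions above. Under B, no secondary endpoint can support a confirmatory claim. B is the smaller edit and stays closer to what 3.4 appears to intend; A is needed if the sponsor wants to claim significance on any of the four.
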